10.2.2 Selection of population

10.2.2.1 Inclusion / exclusion criteria

Inclusion criteria for nintedanib treated patients:

Inclusion criteria:

1. Patients with documented diagnosis of IPF based upon ATS/ERS/JRS/ALAT 2011 guidelines (nintedanib naïve or pirfenidone pre-treated) who have initiated or will initiate nintedanib according to the package insert after the commercial availability of drug in India (23rd January 2017).
2. Patients in whom it is possible to obtain voluntary informed consent either from the patient or patient's legally authorised representative (applicable for Group B and C patients, see [section 10.1](#) for details).

Proprietary confidential information © 2018 Boehringer Ingelheim International GmbH or one or more of its affiliated companies

3. Patients in whom data collection is possible from the medical records (applicable for Group A and B patients, see [section 10.1](#) for details).
4. Patients in whom information on baseline characteristics mentioned in the [section 10.3.3](#) is available.

-Exclusion criteria:

1. Patients who were previously treated with nintedanib.
2. Patients who have initiated or will initiate nintedanib concomitantly with pirfenidone.
3. Patients who are participating in a clinical trial.

Inclusion criteria for pirfenidone treated patients:

Inclusion criteria:

1. Patients with documented diagnosis of IPF based upon ATS/ERS/JRS/ALAT 2011 guidelines (antifibrotic naïve) who have initiated or will initiate pirfenidone according to the package insert after the commercial availability of nintedanib in India (23rd January 2017)
2. Patients in whom it is possible to obtain voluntary informed consent either from the patient or patient's legally authorised representative (applicable for Group II and III patients, see [section 10.1](#) for details).
3. Patients in whom data collection is possible from the medical records (applicable for Group I and II patients, see [section 10.1](#) for details).
4. Patients in whom information on baseline characteristics mentioned in the [section 10.3.3](#) is available.

Exclusion criteria:

1. Patients who were previously treated with nintedanib or pirfenidone.
2. Patients who have initiated or will initiate pirfenidone concomitantly with nintedanib.
3. Patients who are participating in a clinical trial.

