10.9 LIMITATIONS OF THE RESEARCH METHODS

The scientific objective of this active surveillance is to obtain an estimate of the occurrence of all ADRs and SAEs in IPF patients prescribed Nintedanib per the approved label in the real world setting. For retrospective data, there may be a possibility of missed information on adverse events. For patients followed prospectively, lost to follow up, loss of information and recall bias could impose limitations. Since only the cohort treated with Nintedanib will be followed up, it is impossible to assess the safety of Nintedanib compared to other drugs. The possible selection bias will be minimised by enrolling all patients who have initiated or will initiate nintedanib (Group A, B and C) from the date of commercial availability of drug (23rd January 2017) at selected centres and potential channelling bias will be assessed by recording the baseline characteristics of a comparator group of equal number of patients who have been treated with pirfenidone.

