## **6.2 IMPORTANT PROTOCOL VIOLATIONS**

The following table 6.2 defines the different categories of important protocol violations based on protocol versions 5.0. The final column (i.e. Excluded From) in both the tables describes which PVs will be used to exclude patients from the different patients analysis sets.

In this example, patients are either excluded from "All" analysis sets, "Treated Set" or "None" of the analysis sets. The PVs that will not exclude the patient from any analysis set are included for completeness and also to demonstrate a level of quality (or adherence to the protocol). of important PVs but not limited to:

Table 6.2: Important protocol violations

The following table defines the different categories

Category/ code	Description	Requirements	Detected by	Excluded From
A	Entrance criteria not met			
A1	Inclusion criteria not met for patients treated with nintedanib			
A1.1	Patients with documented diagnosis of IPF which is either not based upon ATS/ERS/JRS/ALAT 2011 guidelines (nintedanib naïve or pirfenidone pre-treated) or who have	Patients (nintedanib naïve or pirfenidone pre-treated) whose diagnosis of IPF is not as per the guideline	Manually	None

Category/ code	Description	Requirements	Detected by	Excluded From
	initiated or will initiate nintedanib not according to the package insert after the commercial availability of nintedanib in India (23rd January 2017).	ATS/ERS/JRS/AL AT 2011 and/or who have initiated or will initiate nintedanib not according to the package insert after the commercial availability of nintedanib in India (23rd January 2017).		
A1.2	Patients in whom it is not possible to obtain voluntary informed consent either from the patient or patient's legally authorised representative	Not provided ICF or ICF is provided too late or Missing ICF date.	Automated iPV- Programmatic	All
A1.3	Patients in whom data collection is not possible from the medical records applicable for Group B patients.	No data is collected from medical records or medical records are not available for the Group B patients	Manually	None
A1.4	Patients in whom information on baseline characteristics (which are required for registration procedure) mentioned in the protocol section 10.3.3 is not available.	Baseline characteristics data which is mandatory for the registration process (Section 10.3.3 from Protocol) is not available.	Manually	None

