### **6.3 PATIENT SET ANALYSED**

➤ **Screened Set:**

Screened Set includes all patients who sign the ICF by either voluntarily or patient's legally authorized representative.

➤ **Entered Set:**

Entered Set includes patients in screened set who met the eligibility criteria.

➤ **Treated Set:**

Treated Set includes patients in entered set who have taken at least one dose of nintedanib.

Analysis for all primary and secondary outcomes will be done on treated set.

The following table defines the patient set is to be used for planned analysis.

Table 6.3: 1 Patient sets analyzed

Class of endpoints/outcomes	Patient set		
	Screened Set	Entered Set	Treated Set
Primary and key secondary outcomes (Safety)	-	-	X
(Other) Secondary and further outcomes	-	-	X
Demographic/baseline outcomes	-	X	-

Note: No key secondary and further outcomes mentioned in CTP.

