### **Derivation of Time at Risk in Patients-years for a specific AE**

- Patients with specific AE:

Time at risk (AE) in days = (Start date of first specific AE - Treatment start date) +1

- Patients without specific AE:

Time at risk (AE) in days = Overall time at risk = (End date of time at risk - Treatment start date) +1

Total AE-specific time at risk is derived as below:

Time at risk (AE) [years] = Sum of time at risk [days] across all patients / 365.25

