### **7.8.1 Adverse events**

Adverse events will be collected at the time points or visits specified in flowchart presented in the CTP. The medical records of patients belonging to Group B will be evaluated to see if any ADRs and SAEs have occurred in the nintedanib treated arm during the duration of the treatment before participation in the active surveillance. Group B and Group C patients will be followed up according to clinical practice as per the suggested visit. At each visit, all ADRs associated with nintedanib and SAEs will be recorded and reported.

No adverse events of special interest (AESI) have been defined for this active surveillance.

AEs will be coded using the current version of the Medical Dictionary for Regulatory Activities (MedDRA) version 20.0 or higher and will be based on the concept of treatment emergent AEs. All AEs occurring between first intake of nintedanib prescribed and up to 52 weeks or discontinuation of the drug (or the final contact with the patient for the last regular observation/end of the study) will be considered ‘treatment emergent’. Adverse event summaries will summarize only treatment emergent adverse events (TEAEs), which are defined as AEs not present prior to the nintedanib prescribed.

An AE is considered to be an ADR if either the physician who has reported the AE or the sponsor assesses its causal relationship (at least a reasonable possibility of a causal relationship) between event and drug checked as 'Yes'.

TEAEs will be categorized into one or more of the following categories depending on the type of events reported:

- All TEAEs
- All TEAEs by severity
- All SAEs
- Non-Serious TEAEs
- TEAEs leading to death
- All treatment related TEAEs
- All treatment related SAEs
- All treatment related Non-Serious TEAEs
- All treatment related TEAEs leading to death
- TEAEs leading to Treatment discontinuation
- TEAEs leading to dose reduction
- TEAEs leading to dose interruption

The frequency and incidence rate of AEs/SAEs and ADRs will be tabulated by system organ class and preferred term.

Multiple overlapping or adjacent AE occurrence of same AE are collapsed into one AE event according to BI standard [\(7\)](#).

Two AE are considered to be time-overlapping if the start date of the second, later occurrence is earlier or equal to the end date of the first occurrence.

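### SAP 6.2 and 6.3 disagree on whether Group B patients without medical records are analysed, and the primary ADR and SAE rates pool chart-only with visit-observed time

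*SAP*

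**What the plan says.** **Who is analysed.** Protocol 10.2.2.1 makes usable records an inclusion criterion: "Patients in whom data collection is possible from the medical records (applicable for Group A and B patients". SAP Table 6.2, row A1.3, covers failure of that criterion: "No data is collected from medical records or medical records are not available for the Group B patients". Its Excluded From cell reads None, and the section explains that "The PVs that will not exclude the patient from any analysis set are included for completeness". SAP 6.1, SAP 7.8 and protocol 10.1 likewise take everyone with one dose or more into the safety analysis.

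SAP 6.3 says otherwise: "Entered Set includes patients in screened set who met the eligibility criteria", and "Treated Set includes patients in entered set who have taken at least one dose of nintedanib". All primary and secondary outcomes are analysed on the Treated Set.

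**Where early events come from.** SAP 7.8.1: "The medical records of patients belonging to Group B will be evaluated to see if any ADRs and SAEs have occurred". This refers to treatment before participation, which no study visit covers.

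**How time is counted.** For a patient without the event, SAP 7.4 has "Time at risk (AE) in days = Overall time at risk = (End date of time at risk - Treatment start date) +1". For a patient with the event, the clock also starts at treatment start and stops at first onset. There is no late-entry rule, and SAP 7.7 counts exposure from initiation as well.

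**What is acknowledged.** Protocol 10.9: "For retrospective data, there may be a possibility of missed information on adverse events". SAP 7 plans summaries by Group for basic data such as demographics and disposition. SAP 7.4 and 7.8.1 plan none by Group, or by ascertainment period, for ADRs or SAEs.

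**The concern.** The two primary outcomes are incidences, so the denominator matters as much as the event count. The SAP does not settle whether a Group B patient without chart data is in that denominator. If the patient is in, the pre-participation weeks add person-time and a place in the percentage base, while the planned route for finding events in those weeks has nothing to deliver.

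A weaker form affects every Group B patient whose chart exists but is thin. The rate formula gives a chart-only week the same weight as a week covered by study visits. Non-serious and early-onset ADRs are the most exposed, because they are easily left uncharted and tend to fall before participation. With one pooled figure, a reader of the report cannot separate a low ADR rate from low ascertainment.

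**Working it through.** **No figure to reproduce.** The 200 nintedanib patients are a regulator's request (protocol 10.5). The documents give no event rate, no Group B share and no count of patients without records.

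**Step 1: the passages side by side, for a dosed Group B patient without records.**

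| Rule | In the primary analysis? |
|---|---|
| SAP 6.2, A1.3 marked None | Yes |
| SAP 6.1 and 7.8, protocol 10.1 (one dose or more) | Yes |
| SAP 6.3 with inclusion criterion 3 | No: outside the Entered Set, hence outside the Treated Set |
| Protocol 10.7 (registration procedure not followed) | No, if the missing chart also left registration incomplete |

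The same clash arises for rows A1.1, A1.4 and A2.1 to A2.3. All are eligibility failures marked None.

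**Step 2: effect if the patient is kept.** Documented inputs: N = 200, 52 weeks, clock from treatment start, and rate = 100 × patients with the event / time at risk in years of 365.25 days. Assumed inputs: constant hazard λ, everyone followed for 52 weeks (0.9966 years), and m patients each with u unseen weeks in which nothing is recorded.

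For λ = 0.5 per year, m = 20 and u = 26 (0.4983 years):

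- Fully observed patient: P(event) = 1 − exp(−0.5 × 0.9966) = 0.3924; time at risk = 0.3924 / 0.5 = 0.785 years.
- No-record patient: P(seen event) = 1 − exp(−0.5 × 0.4983) = 0.2205; time = 0.498 unseen + 0.441 observed = 0.939 years.
- Events: 180 × 0.3924 + 20 × 0.2205 = 75.05.
- Patient-years: 141.27 + 18.79 = 160.06.
- Rate: 100 × 75.05 / 160.06 = **46.9** instead of 50. Percentage with the event: 75.05 / 200 = 37.5% instead of 39.2%.

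Range over other assumed values (per 100 patient-years):

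| m | u (weeks) | True rate 20 | True rate 50 |
|---|---|---|---|
| 10 | 12 | 19.7 (−1.3%) | 49.3 (−1.5%) |
| 20 | 26 | 18.9 (−5.5%) | 46.9 (−6.2%) |
| 40 | 26 | 17.8 (−10.9%) | 43.9 (−12.2%) |
| 80 | 40 | 13.5 (−32.7%) | 32.3 (−35.5%) |

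At m = 0 the effect is zero.

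**Step 3: does a participation-date clock repair it?** Under a constant hazard, yes: the 20 patients contribute 20 × 0.441 = 8.82 years, and 100 × 75.05 / 150.1 = 50.0. With early-onset events, only partly. Assume 200 per 100 patient-years in weeks 0 to 12 and 30 afterwards, with m = 20 and u = 26. The true rate is 80.8. The SAP clock gives 71.0, the participation-date clock 76.9, and leaving the patients out 80.8.

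**Step 4: charts that exist but are thin.** Assume a true 52-week ADR percentage of 60%, constant hazard, Group B at half of patients, and entry uniform over the year. Then λ = −ln 0.4 = 0.916, and 1 − 0.6 / 0.916 = 34.5% of Group B have their first ADR before participation. If charts capture 75% or 50% of these, the pooled percentage is 60 − 0.5 × 0.25 × 34.5 = 55.7% or 60 − 0.5 × 0.5 × 34.5 = 51.4%. These losses are upper limits under the stated capture: a patient whose first ADR is missed may still be counted through a later or ongoing one.

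**The case against.** The case for leaving the plan alone has real substance.

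- **The sets already exclude these patients.** A reader of Table 6.2 alone might infer that they stay in every analysis set. SAP 6.3 does not support that. This stands, but it turns the issue into a contradiction rather than removing it, because SAP 6.1, 6.2 and 7.8 still point the other way.
- **The scenario should be rare.** Group B is found by screening medical records, mandatory registration fields would largely come from the chart, and protocol 10.10.1.3.1 lets the investigator request earlier records. This stands: the number is probably small and may be zero. Several registration fields accept an unknown entry, however, and the SAP thought the case worth its own row.
- **Early events are not invisible.** One might infer that no ADR or SAE from the early period could be recorded. Protocol 12.2 requires collection from initiation, so recalled or ongoing events can enter. This stands; recall is incomplete, and resolved non-serious ADRs are the easiest to lose.
- **Sampling error is larger.** With 75 events the approximate 95% half-width is 1.96 / √75 = 23%, against a shift of 6% in the example. True, but the interval does not show a one-directional error.
- **It is disclosed or deferred.** Protocol 10.9 names the limitation, and SAP 6.2 promises a strategy for affected data before database lock. No content is given for that strategy, and a denominator rule is better fixed before the events are known.

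**Conclusion.** The point holds as a contradiction and as a gap in presentation. SAP 6.2 and 6.3 give opposite answers on Group B patients without records. If they are kept, the time-at-risk formula counts weeks whose planned event source is empty. Separately, the primary rates merge chart-only and visit-observed time with no table that lets a reader tell them apart.

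The direction is downward for both primary incidences. The size cannot be derived from the documents. The fall from 50 to 46.9 rests on 20 affected patients, 26 unseen weeks each, a constant hazard and no recall at all. A reader might take the larger falls in the working, to about 51% with any ADR or by a third in the rate, as estimates for this study. They are not: chart capture, Group B share, entry pattern and the number without records are all assumed.

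**What to change.** 1. **Reconcile SAP 6.2 with 6.3.** State for A1.3 whether the patient is in the Entered and Treated Sets, and settle the other eligibility rows marked None by the same rule. Align SAP 6.1 and 7.8 with the result.
2. **If no-record Group B patients are kept,** start their time at risk at the participation date in the rate analysis, list any recalled earlier events, and add a sensitivity analysis without these patients. The sensitivity analysis is needed because late entry does not recover early-onset events.
3. **Present the primary ADR and SAE percentages and rates also by Group (B, C),** and split the Group B rates into pre-participation (chart) and post-participation (visit) person-time. Where first-dose time is kept and a patient leaves risk at the first recorded event, as SAP 7.4 already has it, the two parts add up to the Group B total. The split also needs a line on undated events: SAP 6.6 places a completely missing onset at the consent date, or at the event's end date if earlier, which can move a recalled event towards the visit period.

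Cost: SAP wording and a few table columns, from data already planned for collection. The split tables will have fewer patient-years per cell and so wider intervals.

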### **6.3 PATIENT SET ANALYSED**

➤ **Screened Set:**

Screened Set includes all patients who sign the ICF by either voluntarily or patient's legally authorized representative.

➤ **Entered Set:**

Entered Set includes patients in screened set who met the eligibility criteria.

➤ **Treated Set:**

Treated Set includes patients in entered set who have taken at least one dose of nintedanib.

Analysis for all primary and secondary outcomes will be done on treated set.

The following table defines the patient set is to be used for planned analysis.

Table 6.3: 1 Patient sets analyzed

Class of endpoints/outcomes	Patient set		
	Screened Set	Entered Set	Treated Set
Primary and key secondary outcomes (Safety)	-	-	X
(Other) Secondary and further outcomes	-	-	X
Demographic/baseline outcomes	-	X	-

Note: No key secondary and further outcomes mentioned in CTP.

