10.2.2.3 Patient registration method

In accordance with the inclusion & exclusion criteria, 200 IPF patients who have initiated or will initiate nintedanib (classified as Group A, B and C, see [section 10.1](#)) will be registered. In addition, 200 IPF patients who have initiated or will initiate pirfenidone (classified as Group I, II and III, see [section 10.1](#)) at the same centers and during the same time frame will also be registered.

The medical records at the selected sites will be screened to enroll Group A and B patients in a retrospective manner. Group C patients will be enrolled prospectively. The first patient enrolled at a given site should be in the nintedanib group. Once a patient is enrolled into the nintedanib group, the

site team is suggested to enrol the next eligible patient, who has initiated/will be initiating pirfenidone at the same site in the pirfenidone group.

Patients will be registered by entering following necessary information in the electronic data capture (EDC) system. This information will be mandatory for registration:

- Demographics
- Pulmonary function tests at visit 1 and further visits [FVC, FVC % predicted, FEV1 (mL), FEV1 % predicted, DLCO] – Yes/No/Unknown. If yes specify the values with the dates.
- Family history
- Time since IPF diagnosis (date)
- Chest HRCT evaluation (UIP pattern, Possible UIP pattern, Inconsistent UIP pattern, emphysema)
- Surgical lung biopsy (yes/no/unknown) (UIP pattern, probable UIP pattern, possible UIP pattern, inconsistent with UIP or non-classifiable, not available)
- Previous history of acute exacerbation (Yes/ No/unknown)
- Vital signs and physical examination [Heart rate (beats per minute), blood pressure (systolic blood pressure, diastolic blood pressure) weight and height] - available/not available/unknown, value, date.
- Symptoms
- Known hepatic/renal impairment (yes/no/unknown)
- Comorbidities at visit 1 (yes/no/unknown, if yes specify)
- Bleeding and thrombotic risk (yes/no/unknown)
- Previous medications for IPF (yes/no/unknown, if yes specify)
- Co-medications [at visit 1 and further visits (whether used or not, unknown, start and stop date and dose)]
- Laboratory tests at visit 1 e.g. LFT (performed/not performed/unknown/Performed but missing value and value, date)]

End of registration:

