10.7 DATA ANALYSIS

Analyses will be descriptive in nature including means, medians, standard deviation and interquartile range for continuous variables, and frequencies and percentages for binary and categorical variables with the corresponding 95% confidence intervals. For safety outcomes, incidence rates with corresponding 95% confidence intervals will be calculated. The baseline characteristics of 200 pirfenidone treated patients will be used to compare with the patients profile of the Nintedanib users. Whenever patient profiles differ between those treated with nintedanib and pirfenidone, cautious interpretation is required.

Subgroup analysis will be performed according to prior treatment (see [section 10.7.1](#)).

Any patient who meets the following criteria is treated as ineligible for safety analysis:

- Required registration procedure was not followed

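### SAP 6.3 restricts the primary safety population to eligible patients, while SAP Table 6.2 and the one-dose rule keep dosed patients with entry violations

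*SAP*

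**What the plan says.** SAP 6.3 builds three nested sets. The Screened Set holds patients with a signed consent form. Then "Entered Set includes patients in screened set who met the eligibility criteria", and "Treated Set includes patients in entered set who have taken at least one dose of nintedanib". On use it states "Analysis for all primary and secondary outcomes will be done on treated set". Table 6.3 assigns the baseline summaries to the Entered Set.

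SAP 6.2 sets out a different mechanism. Its final column "describes which PVs will be used to exclude patients from the different patients analysis sets". Rows marked 'None' are there for completeness and to show adherence to the protocol. Only the two consent rows, A1.2 and A3.2, are marked 'All'.

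SAP 6.1, SAP 7.8 and protocol 10.1 each admit patients to the safety analysis on one dose of nintedanib, with no eligibility condition. Protocol 10.7 has one exception. It opens "Any patient who meets the following criteria is treated as ineligible for safety analysis" and lists a single item, failure to follow the required registration procedure. SAP section 4 declares no change from protocol version 5.0.

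**The concern.** The two SAP sections give different answers for the same patient. Take a dosed nintedanib patient who breaches A1.1 (diagnosis or package insert), A1.3, A1.4, A2.1, A2.2 (concomitant pirfenidone) or A2.3 (in a clinical trial). Table 6.2 keeps this patient in every set. Section 6.3 removes the patient from the Entered Set, and so from the Treated Set.

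At stake is who counts in the primary outcomes, the incidence of ADRs and of SAEs. The baseline tables, which serve to compare nintedanib and pirfenidone users, are affected in both cohorts. Two programmers working from different sections would derive different populations. The problem is selection that nobody has declared; loss of precision is secondary.

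**Working it through.** **1. Count of Table 6.2.**

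| Block | Rows | 'All' | 'None' |
|---|---|---|---|
| A1 nintedanib, inclusion | 4 | 1 (A1.2) | 3 |
| A2 nintedanib, exclusion | 3 | 0 | 3 |
| A3 pirfenidone, inclusion | 4 | 1 (A3.2) | 3 |
| A4 pirfenidone, exclusion | 3 | 0 | 3 |
| Total | 14 | 2 | 12 |

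Only nintedanib patients can be in the Treated Set, so 6 of 7 is the count that matters for the outcomes. The 12 of 14 applies to the baseline tables.

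**2. The rules side by side, for a consented and dosed patient with a 'None' violation.**

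| Source | In the safety analysis? |
|---|---|
| SAP 6.3 | No |
| SAP Table 6.2 | Yes |
| SAP 6.1, SAP 7.8 | Yes |
| Protocol 10.1 | Yes |
| Protocol 10.7 | Yes, unless registration was not carried out as required |

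**3. Does another passage decide?** SAP 6.3 does not refer to Table 6.2 or to protocol 10.7. SAP 6.2 promises a strategy for protocol deviations before database lock, but does not say which definition prevails. SAP section 3 also applies the plan to the annual status reports.

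**4. Size.** The documents give no figure to reproduce: no number of violators and no risk among them. Everything below is assumed, except the planned 200 nintedanib patients (protocol 10.5) and the formulas of SAP 7.4.

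*Percentage of patients with an event.* With v violators among 200 treated, p_V their risk and p_E the risk in eligible patients:

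all treated − eligible only = (v/200) × (p_V − p_E)

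| v | Difference −20 points | 0 | +20 points |
|---|---|---|---|
| 5 | −0.5 | 0 | +0.5 |
| 10 | −1.0 | 0 | +1.0 |
| 20 | −2.0 | 0 | +2.0 |

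*Rate per 100 patient-years.* The overall rate is the mean of the two rates weighted by time at risk. With w the violators' share of that time:

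all treated − eligible only = w × (R_V − R_E)

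With R_E = 30 assumed:

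| w | R_V = 15 | R_V = 30 | R_V = 60 |
|---|---|---|---|
| 2.5% | −0.375 | 0 | +0.75 |
| 5% | −0.75 | 0 | +1.5 |
| 10% | −1.5 | 0 | +3.0 |

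*For scale.* Suppose 200 patients, a constant 30 per 100 patient-years, follow-up of 364 days (364/365.25 = 0.9966 years), and time at risk ending at the first event, as SAP 7.4 defines it.

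- Expected cases: 200 × (1 − exp(−0.30 × 0.9966)) = 51.7.
- Time at risk: 51.7/0.30 = 172.3 patient-years.
- Exact 95% interval by the SAP 7.4 formula, for 52 cases in 172.3 patient-years: 22.5 to 39.6.

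Every shift in the rate table is well below the width of that interval.

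**The case against.** The strongest counter-argument is that 6.3 may be carrying out the protocol. Protocol 10.2.2.3 ties registration to the inclusion and exclusion criteria, and 10.7 removes patients not registered as required. On that reading an ineligible patient is a registration failure, and the eligibility filter comes from the protocol. The reading is possible, so a reader who infers that 6.3 certainly breaches the protocol goes too far. It does not rescue the SAP, however: Table 6.2 and the one-dose sentences of 6.1 and 7.8 would then be wrong instead.

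Three other inferences are tempting and not supported.

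- *Row A1.4 must be changed.* The row reads "Baseline characteristics data which is mandatory for the registration process (Section 10.3.3 from Protocol) is not available" and is marked 'None', while protocol 10.2.2.3 says of its list "This information will be mandatory for registration". But many items on that list may be entered as unknown, not available or not performed. Making the entry is mandatory; having a value often is not. 'None' can therefore stand, and a clarification is enough.
- *Manual detection means that the information lies outside the database.* All 12 'None' rows are detected manually, but SAP 6.2 also uses that label for violations too complex to program.
- *The unused 'Treated Set' category shows an intended exclusion.* The introduction to SAP 6.2 announces that category and no row uses it. The sentence is framed as an example and may be leftover template text.

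It is also fair to say that the study is descriptive, and that the pre-lock meeting is the planned place to settle such matters. That postpones the choice until events have been recorded, and does not make it.

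**Conclusion.** Wrong as written. The contradiction within the SAP is certain: 6.3 excludes dosed patients whom Table 6.2, 6.1 and 7.8 keep. A departure from the protocol is likely but not certain, because it depends on how far the registration exception in 10.7 reaches, and neither document says.

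The documents do not support a claim of large bias. In the assumed ranges the shift is at most 2.0 percentage points (20 violators, a 20-point difference in risk), or between −1.5 and +3.0 per 100 patient-years (10% of time at risk, rate ratio 0.5 to 2). It is zero if violators and eligible patients have the same risk. A restriction to eligible patients could be defended from the aim of describing use under the approved label, but it would have to be declared. The point deserves correction because it decides who is in the primary safety analysis and costs little to settle.

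**What to change.** In SAP 6.3 write:

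- *Entered Set: patients in the Screened Set except those with a violation marked 'All' in Table 6.2.*
- *Treated Set: patients in the Entered Set who took at least one dose of nintedanib, except those who fall under the registration exclusion of protocol 10.7. A violation marked 'None' in Table 6.2 is not by itself a registration failure.*

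The last sentence is needed. Without it, the reference to 10.7 could bring the eligibility filter back through protocol 10.2.2.3. It also settles row A1.4 without changing the table.

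If the sponsor instead wants an eligible-only primary population, change the 'None' cells and the one-dose sentences in SAP 6.1 and 7.8, and declare the change in SAP section 4.

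Optionally, show the primary outcomes without eligibility violators as a sensitivity table.

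The cost is SAP wording and a few lines of set derivation, plus one output if the sensitivity table is wanted. The recommended wording needs no protocol change and no new data.
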